Wave reflections can be markedly reduced by organic nitrates, which dilate middle-sized muscular arteries even at doses that do not substantially reduce brachial blood pressure. Our overarching hypothesis is that reducing arterial wave reflections with organic nitrates will reduce LV hypertrophy (a precursor to HF), fibrosis and improve myocardial function in subjects with CKD, independently of blood pressure reduction. Our ultimate goal is to perform an RO1-funded double-blind, parallel-arm, placebo-controlled randomized clinical trial that will enroll patients with CKD and randomize them to either sustained-release isosorbide mononitrate therapy (SR-ISMN) or placebo for 24 weeks.

In this R56-funded study, we aim to obtain key preliminary data for an RO1 resubmission to accomplish a phase IIb randomized controlled trial to test our hypothesis. We wish to obtain: (1) preliminary data regarding the variability in the change of our endpoints in response to our intervention in this specific population; (2) Preliminary data regarding the effects of ISMN on blood pressure vs. wave reflections at different doses; (3) Data supporting the feasibility and local expertise to implement a biomarker discovery approach using proteomics. Our specific aims are:

PRIMARY AIMS: to assess the variability in the response and to perform a dose-response assessment in the degree of change in central hemodynamics and cardiac endpoints with Targeting Central Hemodynamics in CKD Pilot Study
Protocol Version 003, February 15, 2016

ISMN therapy in this population. We propose to administer 3 different doses of SR-ISMN (30, 60 and 120 mg of SR ISMN daily) to 20 subjects with CKD, in order to accomplish the following co-primary aims:

- 1a. To assess the variability in the change in **LV mass** with ISMN administration (**in order to support aim 1a of our eventual RO1-funded trial**). LV mass will be measured with steady-state free precession cardiac MRI.
- 1b. To assess the variability in changes in **diffuse myocardial fibrosis** with ISMN administration, using T1-mapping MRI techniques.⁵⁻¹²
- 1c. To assess the variability in changes in **myocardial systolic and diastolic function** with ISMN administration, assessed via systolic strain (measured with displacement encoded MRI, DENSE) and early diastolic mitral annular velocity (measured with tissue Doppler echocardiography), respectively.

SECONDARY AIMs:

[figure not shown]

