Activity Monitor: Patients will be given an activity monitor to wear during the length of the titration phase, and then for 2 weeks prior to the 12- and 24- week visits (for the latter, the device will be mailed to the subjects 2 weeks prior to the study visit). This device, manufactured by ActiGraph, is a portable, wearable, activity monitor that subjects can wear around their belt. The device records activity information such as the number of steps taken and intensity of the physical activity.

Cardiac MRI: The cardiac MRI protocol will include true-FISP cine acquisitions of the LV for assessment of LV mass. We will assess diffuse myocardial fibrosis by assessing the extracellular volume fraction, computed with the post-gadolinium (0.1 mmol/kgDotarem)

Targeting Central Hemodynamics in CKD Pilot Study
Protocol Version 003, February 15, 2016

normalized myocardial 1/T1 change and the blood 1/T1 change, after correction for hematocrit.^{58, 59} T1 mapping will be performed using a modified Look-Locker inversion recovery (MOLLI)⁶⁰⁻⁶² with image analysis using CMR42 software (CVI42; Canada) and QMass software (Medis Medical Imaging Systems, The Netherlands).

24-hour blood pressure monitoring: will be performed as using a MobileOGraph device (APC cardiovascular, London, UK) or an Oscar 2 device (SunTech Medical) which measures time-resolved brachial arterial pressure estimates arterial wave reflections in an ambulatory fashion based on analysis of the brachial pressure waveform obtained with a cuff. This test will be used to assess potential increases in wave reflections in the nitrate-free period over the nighttime. The Oscar 2 device is FDA approved, but we will use a more advanced version of the device that can record the time-resolved pulse wave from the cuff while blood pressure is being taken. This particular use of the cuff is not FDA approved at present, but we won't be used to guide any clinical decision making. We will also use a novel watch device produced by Microsoft (which is not yet commercially available or FDA-approved), which continuously measures the radial pulse via a mounted tonometer. The device also measures transit time from the heart to the wrist in an ambulatory fashion.

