and 24-weeks). However, echocardiographic and tonometry measures will involve three measurements per subject during the long-term phase (baseline, 12-week and 24-week visit). These will be modeled for intervention effects using general linear modeling on the intent-to-treat population.^{64, 65} Subject-specific intercepts and slopes will be included as random effects; variability in the actual timing of assessments will be explicitly included in the mixed model by analyzing time as a random effect. Individual growth parameters will be modeled as a function of group, time, and the interaction of group and time. Differences in reflection magnitude over time will be examined via inferential testing of the “group by time” interaction term. Restricted maximum likelihood estimation will be used, and an appropriate covariance matrix will be specified. Linear and quadratic mixed models will be examined. The Akaike information criterion⁶⁶ will be used to evaluate overall model fit and to select the best-fitting longitudinal change pattern. For dropouts, the mechanism for missingness will be evaluated. If the number of subjects lost to follow-up is small and the missing observations can be documented as being missing at random (MAR) or missing completely at random (MCAR), analyses will be performed using the complete observed data. More complex approaches will be considered, such as random pattern-mixture models if necessary.^{67, 68} Sensitivity analyses for these models will be performed.⁶⁹ We will use parsimonious linear models to assess whether the reduction in reflection magnitude predicts the improvement in individual outcomes (LV mass, LV collagen volume fraction, LV diastolic relaxation velocity). Bootstrapping procedures will be used to obtain estimates of the effects and to test their significance via confidence intervals.⁷⁰ Analyses will be 1-tailed since we hypothesize specific directions to the relationships or changes in measured parameters between baseline and 24 weeks post-initiation of long-term therapy.

F. PROTECTION OF HUMAN SUBJECTS

F.1. RISKS TO THE SUBJECTS

Human Subjects Involvement and Characteristics

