e. Measures to minimize the risk of breach in confidentiality: All records will be treated with strict confidentiality according to HIPAA guidelines (all study personnel are trained on HIPAA regulations). Blood samples obtained from subjects will be used only for research purposes. Records will be treated with strict confidentiality and stored in a secured, limited access area. A subject ID number rather than name will identify all collected samples and images. A secure database of patient information will be maintained. Only the investigators will have access to research information and will follow IRB and institutional HIPAA guidelines. Paper files will be saved under lock in a secure IRB-approved area.

f. Other measures to minimize risk: Phlebotomy, arterial tonometry and Doppler echocardiographic examinations will only be performed by appropriately trained personnel as per our institutional standards. These procedures will be performed in CTRC-based cardiovascular phenotyping unit at either HUP or Penn Presbyterian medical center.

F.3. POTENTIAL BENEFITS OF THE PROPOSED RESEARCH TO THE SUBJECTS AND OTHERS

There are no anticipated direct benefits to the subjects as a result of their participation in this study nor will this be implied when obtaining consent. However, if our hypothesis is correct, subjects in the active medication groups may experience improvements in their LV hypertrophy and fibrosis, which are associated with the risk of heart failure. However, any potential benefit will not be implied during informed consent or enrollment. The results of this study may ultimately lead to an effective strategy to prevent HF in CKD, which is urgently needed. Since there is minimal risk and potential benefits to medical knowledge and society, the risk / benefit ratio is acceptable.

Overall, the minimal risk to human subjects for participation in this study is greatly Targeting Central Hemodynamics in CKD Pilot Study
Protocol Version 003, February 15, 2016

outweighed by potential scientific knowledge that may result from this work.

F. 4. IMPORTANCE OF THE KNOWLEDGE GAINED

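### Extracellular volume fraction alone cannot tell a change in interstitial amount from a change in cell volume; derive both volumes from the same scans, and correct the fibrosis outcome named in Section D

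*Combined protocol and SAP*

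**What the plan says.** Aim 1b is to assess how variable the change in diffuse myocardial fibrosis is "with ISMN administration, using T1-mapping MRI techniques". Section C.4 (Cardiac MRI) gives the single measure: "We will assess diffuse myocardial fibrosis by assessing the extracellular volume fraction", from MOLLI T1 maps before and after gadolinium, corrected for hematocrit. The same scan supplies LV mass: "The cardiac MRI protocol will include true-FISP cine acquisitions of the LV for assessment of LV mass". MRI is done at baseline and week 24 (C.7 and Appendix II), and hematocrit is drawn before each scan (C.4, Blood Draw).

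The opening hypothesis is that "reducing arterial wave reflections with organic nitrates will reduce LV hypertrophy (a precursor to HF), fibrosis and improve myocardial function". Section F.3 repeats the joint expectation: "subjects in the active medication groups may experience improvements in their LV hypertrophy and fibrosis".

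Section D models whether a reduction in reflection magnitude predicts improvement in three outcomes: "LV mass, LV collagen volume fraction, LV diastolic relaxation velocity". It makes analyses one-tailed in the hypothesised direction, and says that the pilot data will feed power calculations for a definitive trial. Nowhere does the plan derive an absolute extracellular volume or a cellular volume, or say how ECV is to be read alongside LV mass.

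**The concern.** ECV is interstitial volume divided by total myocardial volume. Treatment is expected to reduce the numerator (fibrosis) and also the denominator (LV mass). A change in the ratio then has more than one explanation, and ECV by itself does not identify which applies.

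Three uses of the data are exposed:

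- **Change from baseline to week 24.** A real fall in interstitium can appear as no change or as a rise. With one-tailed analyses, a rise is only a failure to show improvement.
- **The reflection-magnitude model.** If lower reflections mainly shrink cells, the same subjects would improve on LV mass and appear to worsen on fibrosis.
- **Planning the next trial.** If an absolute volume is wanted there, its SD of change cannot be rebuilt from separately reported SDs for ECV and LV mass.

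Separately, Section D names a collagen volume fraction. No procedure in C.4 to C.7 or Appendix II measures collagen; what is measured is ECV.

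**Working it through.** The plan states no expected value, SD or effect size for ECV or LV mass, so there is no figure to reproduce. The check uses the definition of the ratio.

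**Inputs.** From the documents: the measure is a fraction (C.4), and LV mass and fibrosis are both expected to fall (opening hypothesis, F.3). Assumed, because the documents give none: baseline ECV f0 = 0.30 (range 0.25 to 0.35), and the component changes tabulated below.

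**Formulas.** Set baseline myocardial volume to 1, so interstitium I = f0 and cells C = 1 − f0. If I changes by proportion i and C by proportion c:

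- ECV after = f0(1 + i) / [f0(1 + i) + (1 − f0)(1 + c)]
- If interstitium is unchanged and total mass falls by m: ECV after = f0 / (1 − m)
- Total extracellular volume = ECV × LV myocardial volume, so its relative change is i. Tissue density is a constant and cancels.

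**Results at f0 = 0.30**

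| Case | I after | C after | I + C (mass) | ECV after | ECV change, points | Total extracellular volume |
|---|---|---|---|---|---|---|
| Both −10% | 0.270 | 0.630 | 0.900 | 0.300 | 0.00 | −10% |
| Interstitium −5%, cells −10% | 0.285 | 0.630 | 0.915 | 0.311 | +1.15 | −5% |
| Interstitium unchanged, mass −5% | 0.300 | 0.650 | 0.950 | 0.316 | +1.58 | 0% |
| Interstitium unchanged, mass −10% | 0.300 | 0.600 | 0.900 | 0.333 | +3.33 | 0% |
| Interstitium −20%, cells −10% | 0.240 | 0.630 | 0.870 | 0.276 | −2.41 | −20% |

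**Range for baseline ECV 0.25 to 0.35**

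- Proportional shrinkage: exactly 0 at any baseline.
- Interstitium −5%, cells −10%: +1.03 to +1.24 points.
- Interstitium unchanged: +1.3 to +1.8 points for a 5% mass fall, +2.8 to +3.9 for 10%, +4.4 to +6.2 for 15%.
- Interstitium −20%, cells −10%: −2.1 to −2.6 points.

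The direction in each case does not depend on the assumed baseline; the size does. ECV falls only when interstitium shrinks proportionally more than cells.

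**Why two SDs are not enough.** On the log scale, change in total extracellular volume = change in log ECV + change in log LV mass. Its variance is Var(Δ log ECV) + Var(Δ log mass) + 2 Cov(Δ log ECV, Δ log mass). The covariance is within subject, so the volume has to be computed per subject and its SD reported.

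**The case against.** The strongest case on the other side is that nothing is wrong with aim 1b. It concerns the variability of the change, and the SD of change in ECV is the right SD for ECV. Relative interstitial expansion is a coherent target: if cells shrink and matrix does not, the myocardium really is proportionally more interstitial, and ECV reports that correctly. This stands. A reader might infer that ECV is an invalid endpoint, or that it gives the wrong sign. The documents do not support that, because they never define fibrosis as an absolute amount.

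Second, the misleading patterns need cells to shrink at least as much, proportionally, as matrix, and nothing in the documents says that they will. The last row of the table shows ECV falling as intended. This also stands, and it is why only a possibility can be claimed.

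Third, when LV mass falls, ECV understates any absolute decline, so the ratio cannot create a false benefit. That is right where mass falls. It does not cover a subject whose mass rises: with interstitium unchanged and mass up 5%, ECV goes from 0.300 to 0.30/1.05 = 0.286.

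Fourth, total extracellular volume is tied to aim 1a: with ECV constant, its percentage change equals that of LV mass. It also assumes that the sampled ECV represents the whole ventricle, and C.4 does not state the slice coverage of the T1 maps. Both points stand. They are reasons to make the volumes supporting measures and not to replace ECV.

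Finally, the volumes could be derived later from stored data, and Section D promises cautious interpretation. True, but prespecification fixes how a null or rising ECV will be read before results are seen.

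**Conclusion.** The point holds as a limit on interpretation, not as a defect in aim 1b. ECV fraction and its SD of change remain valid for what they measure. What ECV alone cannot do is separate interstitial amount from cell volume when the therapy is expected to change both. Proportional shrinkage reads as zero, and cell-dominant shrinkage reads as a rise that the one-tailed analyses do not test.

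The size in this trial is unknown. The shifts of about 1 to 6 points for cell-dominant shrinkage rest on an assumed baseline ECV of 0.25 to 0.35 and, where interstitium is held constant, assumed mass falls of 5 to 15%. A reader might also infer that the SD carried to the definitive trial will be the wrong one. That cannot be concluded, because the documents do not state that trial's fibrosis endpoint.

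The naming conflict between C.4 and Section D is separate and rests on no assumption: Section D lists an outcome that no procedure measures. Both matters merit correction, and both are cheap to correct.

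**What to change.** - Keep ECV fraction as the aim 1b measure.
- In C.4 and Section D, prespecify two supporting measures per subject from the same scans: total extracellular volume = ECV × LV myocardial volume, and cellular volume = (1 − ECV) × LV myocardial volume. LV myocardial volume is cine LV mass divided by a stated tissue density.
- Report the mean and SD of change of each beside those of ECV and LV mass.
- Add total extracellular volume as a supporting outcome in the reflection-magnitude model.
- State that a null or rising ECV will not be read as absence or worsening of fibrosis without the volumes. If ECV and the volumes disagree, report both and say which component moved.
- In Section D, replace the collagen volume fraction with extracellular volume fraction.
- State the slice coverage of the T1 maps in C.4, since the volumes depend on it.

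The cost is wording and two multiplications per scan. LV mass, T1 maps and hematocrit are already collected at both MRI visits, so no scan, visit or subject is added. The downsides are that the volumes carry LV mass measurement error, assume that the sampled ECV represents the whole LV, are correlated with aim 1a, and lengthen the outcome list.

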Subjects will be recruited from referrals as well as medical record searches (PennSeek). We will enroll adults (age 18 or older) who meet the following criteria:

Inclusion criteria: (1) Chronic kidney disease stage 3 (defined as an estimated glomerular filtration rate [GFR] of 30-59 ml/min/1.73m²), estimated by the CRIC GFR equation⁴³ (2) An elevated left ventricular mass index (defined as >60 g/m^{1.7} in women and 80 g/m^{1.7} in men)³⁸ or LV posterior wall thickness⁴⁴ >1.4 cm documented in a clinically indicated echocardiographic or MRI examination within the previous 24 months; (3) Stable medical therapy as defined by no addition, removal or change in dosage >100% of ACE

inhibitors, angiotensin receptor blockers, beta-blockers, or calcium channel blockers for >30 days; (4) Current therapy with an ACE inhibitor, hydralazine or a statin, all of which have been shown to reduce nitrate tolerance.⁴⁵⁻⁵³

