Exclusion Criteria: (1) A clinically- indicated stress test demonstrating significant myocardial ischemia within 1 year of enrollment, not followed by coronary revascularization; (2) Rhythm other than sinus (i.e., atrial fibrillation); (3) Non-cardiac condition limiting life expectancy to <1 year; (4) Current or anticipated future need for long acting organic nitrate therapy; (5) Severe aortic or mitral valve disease; (6) Hypertrophic cardiomyopathy; (7) Known infiltrative or inflammatory myocardial disease (amyloid, sarcoid); (8) Pericardial disease; (9) Primary pulmonary arteriopathy; (10) History of myocardial infarction, unstable angina, percutaneous transluminal coronary angiography (PTCA) or coronary artery bypass grafting (CABG) within 60 days, or requirement for either PTCA or CABG at the time of consent; (11) Resting heart rate (HR) >100 bpm; (12) A reduced LV ejection fraction (EF<50%); (13) Known severe liver disease (AST >3x normal, alkaline phosphatase or bilirubin >2x normal); (14) Allergy to ISMN; (15) Current therapy with phosphodiesterase inhibitors, such as sildenafil, vardenafil or tadalafil, since the combination of ISMN and phosphodiesterase inhibitors can result in severe hypotension; (16) Therapy with rosiglitazone, since its combination with ISMN is not recommended; (17) Current pregnancy or a positive urine pregnancy test; women who become pregnant during the study will be discontinued from the trial; (18) Therapy with warfarin (as vitamin C may interact with warfarin);^{54, 55} (19) History of kidney stones (as vitamin C may increase the excretion of oxalate); (20) History of G6PD deficiency (as vitamin C may precipitate hemolysis in these patients);^{54, 55} (21) Systolic blood pressure <110 mmHg or diastolic blood pressure <40 mmHg; (22) Contraindications to a cardiac MRI: (a) Central nervous system aneurysm clips; (b) Implanted neural stimulators; (c) Implanted cardiac pacemaker or defibrillator; (d) Cochlear implant; (e) Ocular foreign body (e.g. metal shavings); (f) Other implanted medical devices: (e.g. drug infusion ports); (g) Insulin pump; (h) Metal shrapnel or bullet; (i) Claustrophobia; (j) Extreme obesity rendering the patient unable to fit into narrow-bore scanners; (k) Unwillingness of the patient to undergo a cardiac MRI.

Flow of subjects in the study.

C.4. Baseline assessments

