Blood Draw: Blood samples will be obtained in order to measure serum creatinine and hematocrit prior to each cardiac MRI. In addition, samples will be centrifuged and frozen at -80 degrees C to perform proteomics analysis using the Somascan platform, which measures ~1300 plasma proteins. We will also collect a spot urine sample (~50 cc) in every study visit.

C.5. Run-in phase and ISMN initiation

Subjects will first undergo a run-in phase to assess within subject responses to ISMN at doses of 30 mg, 60 mg and 120 mg daily (with or without ascorbic acid), which will be better powered than between-arm comparisons. Half the subjects will be randomly assigned to receive ascorbic acid (500 mg by mouth three times daily).

- After baseline assessments, ISMN will be initiated at a dose of 30 mg daily (with or without ascorbic acid).
- **1-week visit:** Subjects will undergo a brief visit for peripheral, central BP and arterial stiffness measurements (arterial tonometry and VaSera device measurements) after ~1 week (5-9 days). ISMN will be increased to 60 mg daily. Blood (20 cc) and urine (~50 cc) will also be sampled and frozen.
- **2-week visit:** Subjects will undergo a brief visit for peripheral, central BP and arterial stiffness measurements (arterial tonometry and VaSera device

measurements) after ~1 week (5-9 days). ISMN will be increased to 120 mg daily. Blood (20 cc) and urine (~50 cc) will also be sampled and frozen.

- **3-week visit:** Subjects will undergo a brief visit for peripheral, central BP and arterial stiffness measurements (arterial tonometry and VaSera device measurements) after ~1 week (5-9 days). Subjects will also undergo a Doppler echocardiogram during this visit. A 24 hour ambulatory BP monitoring Blood (20 cc) and urine (~50 cc) will also be sampled and frozen.

In all cases, up-titration will occur only if:

- (1) Resting supine systolic blood pressure is ≥ 95 mmHg;
- (2) There is no evidence of orthostatic hypotension (decrease ≥ 20 mmHg in systolic or ≥ 10 mmHg in diastolic blood pressure within 3 minutes of standing);⁶³
- (3) The subject is not experiencing dizziness, vertigo, or other symptoms that, in the opinion of the investigator, may be due to the vasoactive effect of the drugs.

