c. Protection against risks associated with gadolinium contrast: Serum creatinine will be measured prior to each scan to assure adequate renal function for the administration of gadolinium-based contrast as per our inclusion/exclusion criteria. Pregnancy status will be determined for all women of childbearing age before enrollment and before the final MRI scan. Pregnant women will be excluded and/or discontinued from the study. Subjects will not receive two injections of gadolinium within one week of each other as frequent use of gadolinium can cause nephrogenic systemic fibrosis (NSF). If a subject has recently received an MRI for clinical purposes, the research MRI will be delayed to avoid the second injection of gadolinium within the one week-timeframe.

d. Protection against risks of study medications: To reduce the risk of hypotension and related side effect, participants will be instructed to get up slowly when rising from a sitting or lying position. The study team will specifically assess for the presence of Targeting Central Hemodynamics in CKD Pilot Study

Protocol Version 003, February 15, 2016

hypotension and orthostatic hypotension, as well as symptoms such as dizziness after the medication is initiated or after the dose is increased, in order to determine whether it is safe for participants to continue taking these medications, or to uptitrate the dose. If participants find these side effects too uncomfortable, they will be deemed intolerant to the drugs and discontinued from the study. Study subjects can always withdraw from the study at any time and this will be made clear to them. We will specifically exclude individuals who are taking sildenafil (Viagra®), tadalafil (Cialis®), or vardenafil (Levitra®) and we will instruct them not to take these medications while participating in the study, as well as the risks associated with this combination. If subjects express the wish to take these medications within the 24 weeks following consent, they will not be included in the study. We will exclude subjects with a history of kidney stones, since vitamin C may precipitate the recurrence of oxalate kidney stones. We will also exclude patients with G6PD deficiency, since vitamin C may precipitate hemolysis in this condition.^{72, 73}

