APPENDIX II

List of procedures / visits and schedule of events

A. List of procedures per visit

Baseline Visit	
• Read and sign this informed consent form (ICF).• If you are a pre-menopausal woman, confirm that you are not pregnant by a urine pregnancy test.• Have a medical history assessment, a physical, and record vital signs.• Have your blood drawn and collect urine.• Arterial Tonometry / VaSera test.• Have a Doppler Echocardiogram.• Complete the MRI of your Heart.• Setup the 24 Hour BP monitoring and pulse wave analysis watch.• Medication given out.• Bicycle Exercise Test• Activity Monitor
Week 1 Visit	
• Collect Vital Signs.• Review Side Effects• Increase medication dose to 60 mg daily.• Collect medication of the previous dose.• Arterial Tonometry / VaSera test.• Download and replacement of pulse wave analysis watch• Blood draw and urine collection• 24 Hour BP Monitoring• Activity Monitor
Week 2 Visit	
• Collect Vital Signs.• Review Side Effects• Increase medication dose to 120 mg daily.• Collect medication of the previous dose.• Download and replacement of pulse wave analysis watch• Collect information on potential side effects.• Arterial Tonometry / VaSera test.• Replace pulse wave analysis watch.

	
 • Medication given out. • Arterial Tonometry and VaSera • 24 Hour BP Monitoring • Activity Monitor
Week 3 Visit	
 • Collect Vital Signs. • Review Side Effects • 24 Hour BP Monitoring and pulse wave analysis watch Arterial Tonometry / VaSera test. • Have a Doppler Echocardiogram. • Bicycle Exercise Test • Blood Draw and urine collection • Activity Monitor: 2 weeks prior visit
3 Month Visit	
 • The Arterial Tonometry and VaSera test. • Have a Doppler Echocardiogram. • Setup the 24 Hour BP monitoring and pulse wave analysis watch. • Medication given out. • Activity Monitor: 2 weeks prior to the visit • Review Side Effects • Blood Draw and urine collection

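### No standing blood pressure is required before the first 30 mg ISMN dose, so a pre-existing orthostatic fall can go unseen until week 1 and a first positive test then cannot be classed as new or old

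*Combined protocol and SAP*

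**What the plan says.** Section C.5 sets the starting rule and the escalation rule. The start is tied only to completion of baseline work: "After baseline assessments, ISMN will be initiated at a dose of 30 mg daily". Each later step up needs three things: a supine systolic pressure of at least 95 mmHg, no suggestive symptoms, and a standing test, worded as "There is no evidence of orthostatic hypotension". That test is defined as a drop of 20 mmHg or more systolic, or 10 mmHg or more diastolic, in the first three minutes upright. These conditions are stated for up-titration and not for initiation.

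Section F.2.d also commits the team to look for orthostatic hypotension, but times this "after the medication is initiated or after the dose is increased, in order to determine whether it is safe for participants to continue".

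At entry, Section C.3 excludes subjects by resting values alone: "21) Systolic blood pressure <110 mmHg or diastolic blood pressure <40 mmHg". It gives no posture, and orthostatic hypotension is not itself an exclusion. Appendix II asks at baseline to "Have a medical history assessment, a physical, and record vital signs", and at weeks 1 and 2 to "Collect Vital Signs".

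On background therapy, Section C.3 admits subjects on stable "angiotensin receptor blockers, beta-blockers, or calcium channel blockers for >30 days" and requires "Current therapy with an ACE inhibitor, hydralazine or a statin". Hydralazine, itself a vasodilator, is therefore a qualifying drug. There is no upper age limit.

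**The concern.** The protocol treats a postural fall as reason enough to withhold a dose increase, yet does not ask whether one is present before a vasodilator is first given. The appended label makes this relevant to the enrolled population. It warns of severe upright hypotension even at low doses (Precautions), of marked symptomatic orthostatic hypotension when nitrates are combined with calcium channel blockers (Drug Interactions), and of severe orthostatic hypotension in elderly patients given vasodilators (Geriatric Use).

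Two things are at stake. The first is safety: a subject with an unrecognised fall may start treatment and remain on it for about a week before anyone is obliged to measure it. The second is interpretation of the week 1 test. The drug-free standing reading cannot be obtained once dosing has begun, and it would help the Section F.2.d judgement on whether continuing is safe.

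**Working it through.** No planned figure (alpha, power or sample size) is involved, so the check is mainly a comparison of the text.

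**Step 1. Is a standing reading required anywhere before the first dose?**

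| Place | What it requires | Standing reading before first dose? |
|---|---|---|
| C.3, exclusion 21 | Systolic and diastolic limits, posture not given | No |
| C.4, tonometry | Oscillometric brachial pressure | No |
| C.4, 24-hour monitoring | Ambulatory pressure, no posture procedure | No |
| C.5, start of ISMN | Baseline assessments completed | No |
| C.5, up-titration rule | Supine and standing test | Applies to dose increases only |
| F.2.d | Orthostatic assessment | After initiation or a dose increase |
| G.1 | Side effects followed at visits and calls | No |
| Appendix II, baseline | History, physical, vital signs | Not specified |

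Appendix II does not settle the matter alone. It uses the same general term at weeks 1 and 2, where C.5 makes the standing test mandatory. The gap rests on C.5 and F.2.d. A site could take a standing reading at baseline by choice, but nothing obliges it to.

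**Step 2. Exposure before the first mandated check.** Inputs: one 30 mg dose a day, and a week 1 visit after 5 to 9 days (both C.5).

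- Doses: 1 per day × 5 to 9 days = about 5 to 9 doses.
- Time: 5 × 24 = 120 hours to 9 × 24 = 216 hours.
- For comparison, the label table in Appendix I puts the peak level after a single 60 mg extended-release tablet at 3.1 to 4.5 hours. This is a different dose and serves only as a guide, but the first peak falls well before the first check.

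**Step 3. Which positive tests cannot be classified?**

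- Week 1, on 30 mg: no earlier standing test exists. A positive result may be new or may have been present at baseline.
- Week 2, on 60 mg: the subject reached 60 mg only after a negative test on 30 mg. A positive result is new since that test.
- Week 3, on 120 mg: the subject reached 120 mg only after a negative test on 60 mg. The same applies.

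The ambiguity therefore lies mainly in a first positive at week 1.

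**Step 4. What would happen to a subject whose fall persists?** C.5 assigns only 60 or 120 mg for the 21-week phase. Both lie above 30 mg and require the subject to pass the standing criterion. A subject whose fall of 20/10 mmHg or more persists would be exposed to 30 mg but could not move to either long-term dose.

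**Step 5. How many subjects?** The documents give no prevalence of orthostatic hypotension. Under a purely assumed prevalence p, the expected number among 20 is 20p, and the chance of at least one is 1 − (1 − p)^20:

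- p = 5%: 1 subject; 64.2%
- p = 10%: 2 subjects; 87.8%
- p = 20%: 4 subjects; 98.8%
- p = 30%: 6 subjects; 99.9%

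These lines show only how the answer moves with the assumption. They are not an estimate for this trial.

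**The case against.** The strongest reply is that starting as written follows the label. The label recommends 30 or 60 mg as the starting dose and the protocol takes the lower. Its caution about patients who are already hypotensive is met in part by exclusion 21. Subjects are told to rise slowly, history and a physical are taken, and symptoms are followed. None of the label's warnings asks for a standing measurement before the first dose. All of this stands, and it is why the point is an inexpensive improvement and not a breach of any standard in the documents. It does not remove the gap, because none of these steps detects a fall on standing.

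A reader might infer four stronger things that the documents do not support.

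- **That starting is held to a looser standard overall, or that the protocol contradicts itself.** Entry requires a systolic pressure of at least 110 mmHg, while escalation requires only 95 mmHg supine. The escalation rule would itself pass a supine 95 with a 19 mmHg fall, which is 95 − 19 = 76 mmHg standing. A stricter postural rule for escalating is not inconsistent. Pointing to an eligible subject at 110/40 who falls to 90/30 adds little, since it needs both limits to be met at once.
- **That every fall at weeks 1 to 3 is unclassifiable.** The up-titration rule supplies a negative test before each higher dose.
- **That a baseline reading would show whether the drug caused a fall.** There is no nitrate-free group, so it would separate new from pre-existing and no more.
- **That the hazard is large.** In the label's North American trials, dizziness occurred in 8% of 60 patients on 30 mg and 4% of 96 on placebo, and 0% of those on 30 mg stopped because of it. Dizziness is not orthostatic hypotension, so these figures size the risk in neither direction, but they give no ground for alarm.

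**Conclusion.** The point holds in limited form. The protocol requires the standing test before each dose increase but not before the first dose. The consequences are about 5 to 9 daily doses before the first mandated check in a subject with an unrecognised fall, and a week 1 positive that cannot be called new or pre-existing.

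The conclusion assumes that baseline vital signs and the physical do not by unwritten custom include a standing reading, and that no standing check takes place before the week 1 visit. Whatever sites do in practice, the text does not require one. The number of subjects affected is unknown. No stated aim, endpoint or analysis changes. Priority is minor.

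**What to change.** - At the baseline visit, before medication is handed out, take the supine and three-minute standing measurement already defined in C.5.
- If the fall is at least 20 mmHg systolic or 10 mmHg diastolic, hold dispensing and repeat the measurement. If it persists, do not start. Allowing a start at the investigator's discretion would be a weaker rule, because the same criterion would later bar the subject from both long-term doses.
- Leave the up-titration rule as it is.
- Name the supine-to-standing measurement in Appendix II at baseline and at weeks 1 and 2, where the escalation rule applies.

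The cost is a few minutes per subject at a visit that already records vital signs, a short amendment to C.5 and one line in the schedule. An occasional subject may not be started, and the documents give no basis for predicting how many.
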